11.2. SAMPLE SIZE CONSIDERATIONS

Taking into consideration a possible 20% dropout during the study, our sample size of 30 patients per group is a conservative number. For comparing two groups in Aim1 and Aim2, a sample size of 24 in each group will have 80% power to detect an effect size of 1.2 using a two-group t-test with a 0.05 two-sided significance level. For Aim3, baseline vs placebo/active M1 HD-tDCS, a sample size of 24 will have 80% power to detect an effect size of 0.8 using a paired t-test with a 0.05 two-sided significance level, allowing a wide range (0.1 to 1.0) of observable correlations within pairs.

Using the previous study, we approximated the SD as 20%/4 = 5% (range/4), and this gives us a detectable percentage change of 5*0.8=4 or higher.

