4. STUDY DESIGN

This is a phase 2, single center, three-arm, double-masked, randomized investigation of the modulation of the μ -opioid mechanisms in episodic migraine (in vivo).

The population for the study will consist of 60 patients with episodic migraine (30 for the active M1 HD-tDCS group and 30 for the placebo HD-tDCS group). In addition, we will use the data from up to 10 healthy controls who were recruited and scanned during the NINDS-K23062946 project (IRBMED #HUM00027383; [name], Principal Investigator). We will then recruit healthy volunteers to a total of 30 age- and gender-matched healthy subjects.

All subjects will be enrolled as either episodic migraine or healthy volunteers (HV; N=90); if episodic migraine (n=60), they will be randomized to one of two treatment arms: active (n=30) or sham (n=30).

Each participant will undergo the sequence of events and evaluations laid out in the Schematics of Study Design (Protocol Summary; pages vii-viii), which will take approximately 3 months. Completion of full protocol enrollment and participation is expected to take approximately 5 years.

Data will be collected either on paper or electronic CRFs (most questionnaires, screening/demographic and logistical information regarding assessments) or electronically on local systems(PET, MRI, HD-tDCS), then transferred via HIPAA-compliant methods within the UMHS system for analysis by study staff.

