5.6. HANDLING OF WITHDRAWALS

Subjects wishing to withdraw from the study at any time may notify the study team.

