8.1.4. TRANSCRANIAL DIRECT CURRENT STIMULATION (TDCS)

We will conduct a single-center, sham-controlled, single-blinded study to prospectively investigate the neuromodulatory effects of M1 HD-tDCS in pain intensity and brain molecular neuroplasticity in a cohort of episodic migraine patients. The patients will participate in 10 daily sessions—5 daily sessions each weekday for two consecutive weeks—of either active or sham M1 HD-tDCS. (Figure 10). If a patient misses the day of a tDCS session, two tDCS sessions will occur the following day. tDCS sessions will be conducted at the University of Michigan Health System (eg, Michigan Clinical Research Center, Center for Human Growth and Development). Before and after each tDCS session patients will complete pain and mood questionnaires.

Prior to brain stimulation, the subject's scalp will be prepped in the M1 area contralateral to the subject's worst pain. The vertex will be found by measuring the midpoint between nasion and inion and the midpoint between the pre-auricular areas. Then the midpoint from the vertex to the pre-auricular point, on the side contralateral to the patient's worst pain, will be marked so that stimulation can be applied to the same spot each day. Alcohol pads will be used to wipe a 4 cm x 4 cm square centered over the motor cortex, followed by the application of approximately 6 mL of aloe vera gel to hydrate the scalp.

After 5 minutes have passed, the scalp will be wiped with gauze to remove excess gel. A perforated cloth cap with a chinstrap will then be placed on the head; this will secure plastic casings in the desired position of each electrode. Approximately 1 mL of Lectron II Conductivity Gel will be injected into each electrode casing slot. Four electrodes will be placed, with the upper anode placed on C3 and lower anode on C5, and the upper and lower cathodes placed anteriorly on FC3 and FC5, respectively, using the International Electroencephalography (EEG) 10-20 system (Zaghi et al., 2010). Approximately 1 mL of additional gel will be injected into the electrode casings. Ag/AgCI sintered ring electrodes with the rough surface directed towards the skin will be placed into the gel and held in place with plastic caps. The electrode wires will be held in place with a light adhesive tape (eg, Scotch tape), and the contact quality tested. Procedures will be reviewed with the subject before proceeding

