11. STATISTICAL CONSIDERATIONS

The main contrasts of interest will be modeled using both volume-of-interest (VOI) data with SPSS and parametric statistical maps using the SPM8 package and a general linear model for the radiotracers. The main effect of interest [effect of acute and chronic pain, opioid and psychophysiological measures, before and after 10 M1 HD-tDCS sessions (active or sham) can be modeled by t-tests or ANOVA (e.g., effect of pain), or ANCOVA (with age as covariate), with post-hoc t-tests to determine the direction and magnitude of regional changes. However, a global model will also be utilized to determine the main effects of pain, and interactions with sex and other nuisance variables (e.g., age). In that manner, we will examine the main effects of migraine and repetitive M1 HD-tDCS neuromodulation on receptor BP_{ND}, BP_{ND} changes in the thalamus and other pain-related regions in response to an experimental pain challenge, interrelationships between variables, and additional interactions with covariates of interest and nuisance variables.

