Feasibility: (Aim 3.1) We conducted analysis to demonstrate that tDCS can significantly modulate μ-opioid mechanisms and trigeminal pain measures in vivo, even immediately. This is a unique advance in pain translation research in humans, previously only possible in animal models. We examined with PET nine healthy volunteers with no history of chronic pain or systemic disorders. The protocol consisted of two PET scans, using [11C]carfentanil, a selective µOR radiotracer (Figure 17). The first PET provided a baseline evaluation of regional µOR BPND. During the second PET, placebo and active (2mA) M1-SO tDCS sessions were delivered sequentially, 20 min each, the same M1-SO tDCS montage as in our proposed migraine study. When analyzed separately, placebo and active tDCS were both associated with an acute reduction in µOR BPND, indicating activation of this neurotransmitter system in the PAG. In addition, the initial sham tDCS phase induced immediate activation of µORs in the left thalamus (Thal) and post-cingulate cortex, (PCC) and subsequently during the active tDCS phase in the left pre-frontal cortex (PreF) and precuneus (PreC). However, only after active tDCS was there significant improvement of pain thresholds measured by quantitative sensory testing, which were correlated with µOR system activation (DosSantos et al., 2014b). Our results suggest that immediate global analgesia induced by the M1-SO tDCS application, sham and active, can be related to the recruitment of endogenous muopioid mechanisms.

Analysis: (Aim3) First, we will examine changes in baseline μ OR BPND and in the activation of μ -opioid neurotransmission between pre- and post- 10 active daily HD-tDCS treatments. A mixed model of variance, accounting for age and other potentially influencing variables (e.g., plasma levels of estradiol, testosterone) will be employed. Increases in baseline μ OR BPND and in the activation of μ -opioid neurotransmission from pre- to post- 10 HD-tDCS sessions in migraine will be expected, with an approximation towards control values. The Spearman nonparametric test will then be used to assess the correlation between the percentage of change pre- and post- 10 M1-tDCS sessions in the thalamus and each region where it was observed, and that of the acute and chronic pain relief.

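### Aim 2 is sized and tested on patients who remain, with no stated rule that every randomised patient is analysed in the assigned arm

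*Combined protocol and SAP*

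**What the plan says.** Section 4 sets up the randomised part of the study: migraine patients enter and "they will be randomized to one of two treatment arms: active (n=30) or sham (n=30". Aim 2 compares these two arms on pain.

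Section 11.2 gives the sample size: "Taking into consideration a possible 20% dropout during the study, our sample size of 30 patients per group is a conservative number". For Aims 1 and 2 it states that "a sample size of 24 in each group will have 80% power to detect an effect size of 1.2". The test behind that statement is a t-test between two groups, two-sided at the 0.05 level.

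Section 11 says that the main effects "can be modeled by t-tests or ANOVA (e.g., effect of pain), or ANCOVA (with age as covariate"), and it adds a global model that is not specified further. Section 11.1 has an analysis paragraph for Aim 1 and one for Aim 3, but none for Aim 2. The Aim 3 paragraph describes changes "between pre- and post- 10 active daily HD-tDCS treatments" and names a mixed model first, then a Spearman correlation of percentage changes.

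On leaving the study, section 5.6 consists of one sentence: "Subjects wishing to withdraw from the study at any time may notify the study team". The early termination visit in section 7.6 records adverse events and final instructions, with no pain outcome.

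On data, section 8.1.4 says "Before and after each tDCS session patients will complete pain and mood questionnaires". Appendix A schedules the pain scale, GeoPain and the short McGill form at the sessions and at Week 1, Month 1 and Month 2.

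Section 11.6 leaves the final analysis to a Statistical Analysis Plan, which the list of supplemental materials places outside the protocol. It is not in the supplied text.

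**The concern.** A t-test or ANCOVA on a post-treatment value uses only patients who have that value. Section 11.2 carries 24 rather than 30 per arm into the power statement, which suggests that this is the population it has in mind. Aim 2 is the study's randomised treatment comparison, and randomisation protects a comparison of the arms as allocated, not of those who stay.

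Suppose that patients leave because stimulation is not helping. More would then leave sham than active, the remaining sham patients would look better than the sham arm as a whole, and the difference between arms would be understated. Leaving because of side effects in the active arm could push the other way. The plan has information that would reduce the problem, because patients who leave during or after stimulation have already given pain scores. The tests it names do not use them.

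**Working it through.** **Inputs from the protocol.** 30 per arm (section 4); 20% dropout, 24 per group, effect size 1.2, 80% power, two-sided 0.05, two-group t-test (section 11.2); 10 sessions with questionnaires before and after each (section 8.1.4).

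**Dropout allowance.** 24 / (1 - 0.20) = 30 per group, so the plan's figure reproduces. Planned losses are 0.20 × 30 = 6 per arm, or 12 of 60.

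**Data left unused.** 10 sessions × 2 = up to 20 session-day pain scores per patient, fewer for a patient who leaves in mid-course. Patients who leave later also have some follow-up scores.

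**What 24 per group can detect.** By the noncentral t distribution, 24 per group at two-sided 0.05 has 80% power at 0.826 SD. With outcomes on all 30 the figure is 0.74 SD. At an effect of 1.2, 24 per group has 98.3% power rather than the stated 80%. That is a separate discrepancy. It matters here only because the consequences of dropout depend on which effect is taken as true. Section 11.1 cites a meta-analytic effect of -0.86 on the pain scale, which is close to 0.826.

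**How the bias arises.** In one arm with dropout fraction p, the arm mean is (1 - p) × completer mean + p × dropout mean. Hence completer mean - arm mean = p × (completer mean - dropout mean). The bias of the contrast is the difference between the two arms' shifts. With p = 0.20 and a gap of 0.25 to 1.0 SD in one arm only (assumed), it is 0.20 × 0.25 = 0.05 to 0.20 × 1.0 = 0.20 SD. With the same shift in both arms it is zero.

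**Illustrative simulation.** Assumptions, none of them in the documents:
- 30 per arm and 4,000 trials per setting.
- Overall dropout 20%, driven by the on-treatment pain score, with log-odds slope 1 or 2 per SD.
- On-treatment pain already lower in the active arm.
- Correlation 0.5 to 0.85 between on-treatment and follow-up pain.

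| True effect | Completer t-test |
|---|---|
| 0.826 SD | estimate about 0.67 to 0.78 SD; power about 70 to 75% |
| 1.2 SD (the plan's) | power about 94 to 97% |
| none | type I error near 5% |

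At 0.826 SD the relative bias is (0.67 - 0.826) / 0.826 = -19% to (0.78 - 0.826) / 0.826 = -6%. Dropout comes out at 25 to 28% in sham and 12 to 15% in active. With slope 0, so that dropout is unrelated to pain, the completer estimate is unbiased and power is about 80%. A likelihood estimate that uses everyone's on-treatment score gives 0.82 to 0.83 SD. That result follows from the set-up, because dropout was made to depend only on observed scores. It shows what the method does when its assumption holds, and is not evidence that the assumption holds here.

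**The case against.** The strongest objection is that the Statistical Analysis Plan has not been seen. Analysis sets and missing-data rules usually sit there, so the gap can be asserted only for the supplied text. That stands. Section 11 is also permissive about methods and mentions a global model, so a completer analysis is the default implied by the named tests and the sizing. It is not a stated intention.

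Differential dropout is not documented either. Section 11.1 reports that all 24 randomised patients completed the group's 5-session trial in temporomandibular disorder, section 2.3.1 reports no one abandoning a tDCS study through discomfort, and section 11.2 calls 20% only possible. This limits how likely the problem is. It does not remove the need for a rule, since the plan itself allows for the loss of 6 per arm.

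Three stronger readings are tempting and are not supported:
- *That patients with fewer than 10 sessions are excluded.* The aims name a 10-session regimen, but no passage makes completing it a condition of analysis. Visits are set by calendar day, so a patient with fewer sessions can still attend them.
- *That Aim 3 loses a randomised comparison in the same way.* Its analysis is written as a change before and after active treatment and sized with a paired t-test, so there is no clear randomised contrast to lose. The mixed model named first can retain patients with one scan.
- *That dropout here would create false positives.* Under the simulated mechanism it does not. Type I error of 8 to 21% appeared only under a different assumption, with outcome-related dropout in one arm alone.

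**Conclusion.** The point holds for Aim 2. In the supplied text the randomised pain comparison is sized and tested on those who remain, no as-randomised rule is given, and the named tests leave scheduled pain scores unused. The size of any bias cannot be derived from the documents. The simulated figures are illustrative: they depend on the assumed link between dropout and on-treatment pain, on the correlations and on a true effect of 0.826 SD. At that effect they amount to an understatement of 6 to 19% and a modest loss of power. At the plan's 1.2 the loss of power hardly matters, although the estimate would still be biased under the same mechanism. If dropout is unrelated to pain there is no bias. For Aim 3 the remaining issue is only who enters the model. The change is worth making because it is cheap and makes better use of the data, not because bias has been shown.

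**What to change.** In sections 11.1 and 11.2, and in the Statistical Analysis Plan if it does not already say so:

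1. State that Aim 2 includes every randomised migraine patient in the assigned arm, whatever the number of sessions received.
2. Add an Aim 2 analysis paragraph naming a likelihood-based repeated-measures model with arm, visit, arm by visit and baseline. Fit it to the pain scores already scheduled at Week 1, Month 1 and Month 2, with on-treatment scores summarised, for example by week, so that early leavers contribute.
3. Keep the completer t-test as a sensitivity analysis.
4. For Aim 3, state only that patients with the first PET scan alone stay in the mixed model already named. The Spearman analysis necessarily needs both scans.

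The cost is wording and a standard model, with no new visits, measurements or patients. There are two drawbacks. The model relies on data being missing at random given the observed scores. In addition, many session-day scores may be zero in episodic migraine, where the entry criterion is fewer than 15 attacks a month. That is why weekly summaries are suggested rather than up to 20 separate scores, and the distribution of the summaries should be checked before the model is fixed.

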migraine patients are associated with μOR BP_{ND} in the thalamus and other pain-related regions, even during interictal phase

(non-headache phase).

To determine whether 10 daily sessions of M1 HD-tDCS have modulatory effect on clinical and experimental pain measures in

migraine patients.

To investigate whether repetitive active M1 modulation induces/reverts thalamic µOR BP_{ND}, and whether those changes are associated with clinical and experimental pain

measures in migraine patients.

Population: 60 Patients age 18-65 years (inclusive) with episodic migraine

(ICHD-3-beta); AND

30 age and gender matched healthy subjects

Subjects will be recruited from the UMClinicalStudies.org database, the clinics at the University of Michigan (UM), and

from other clinics in the region

Phase: 2

Number of Sites: 1

Study Duration: 5 YRS

Investigation and Modulation of the Mu-Opioid Mechanisms in Migraine (In Vivo) Protocol HUM00107286 Version 0.6 12 December 2018

Subject Participation

Approximately 3 Months

Duration:

Description of Agent High-de

or Intervention:

High-definition transcranial direct current stimulation (HD-

tDCS)

Estimated Time to

4 Years

Complete Enrollment:

Schematic of Study Design I:

Screening Period	Week before daily M1 HD-tDCS sessions (Neuromodulation)	Active / Sham Neuromodulation (10 Daily Sessions) M-F x2		Week after daily M1 HD-tDCS sessions	Follow-up Period ⇒
First Appt	PET/MRI Sessions	5 Daily Sessions	5 Daily Sessions	PET/MRI Sessions	Follow-up at 1 Week and at 1 Month and 2 Months Following Neuromodulation

.....

Schematic of Study Design II:

Timing (Relative to Day 0)	Procedure		
PreScreening (Up to 8 weeks prior to Day 0)	Phone Call: IRB-Approved Prescreening Checklist/Script		
Screening (Up to 3 weeks prior to Day 0)	Informed Consent Demographics History and Physical Exam Questionnaires Randomization, once subjects have been consented		
PET and MRI #1 (Up to 1 week prior to Day 0)	QST PET #1 Workup Questionnaires (PET-specific) Pregnancy Test and Drug Screen CFN (11C-carfentanil) Injection MRI #1 Screening Form (MRI-specific) MRI Questionnaires*		
HD-tDCS x 10 Daily Sessions (Day 0 - 11; Week 1 and 2)	Migraine Active Questionnaires ≤2 mA current for 20 min/day x 10 days (M-F over 2 wks)	Migraine Sham Control Questionnaires ≤2 mA current for 30 sec at start plus 30 sec at end of session x 10 days (M-F over 2 wks)	* Healthy volunteers complete participation after PET/MRI#1 visit

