14.4. EXCLUSION OF WOMEN, MINORITIES, AND CHILDREN (SPECIAL POPULATIONS)

We will recruit and study a total of 60 patients diagnosed with episodic migraine, and 20 gender- and age-matched healthy controls, 18-65 years old (inclusive), during the 5-year course of the study. We will use the demographic and PET/MRI data from 10 additional healthy controls, who were recruited and scanned during the NINDS-K23-NS062946 project. Women and men will be recruited at a ratio of 3:1 to reflect the gender ratio prevalence of migraine in our population.

We will recruit without regard to ethnicity, and anticipate that this will reflect the racial characteristics of the general population in this region of the country. According to 2000 census data, the demographic composition of Washtenaw County is 75% White, 12% Black, 5% Asian/Pacific Islanders, 12% Hispanic or Latino (of any race), <1% American Indian/Eskimo/Aleut, and 1% Other.

We are proposing to study subjects between the ages of 18-65. Young children would be unable to participate because of blood volume limits and the utilization of ionizing radiation (PET). We draw up to 120 ml of blood in these studies, which is over the allowable guidelines for younger children. In addition, we utilize daily sessions of HD-tDCS that require careful monitoring of internal states and accurate reporting, which may be difficult to tolerate and perform for children.

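### Section 11.2 sizes the primary Aim 1 comparison as 24 v 24, but by design it compares up to 60 migraine patients with up to 30 controls at the first scan; the stated effect size of 1.2 fits neither

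*Combined protocol and SAP*

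**What the plan says.** Section 11.2 starts from 30 per group and allows for loss: "Taking into consideration a possible 20% dropout during the study, our sample size of 30 patients per group is a conservative number". It then covers two aims in one sentence: "For comparing two groups in Aim1 and Aim2, a sample size of 24 in each group will have 80% power". The sensitivity attached is "80% power to detect an effect size of 1.2 using a two-group t-test with a 0.05 two-sided significance level".

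The two aims contrast different groups. Aim 2 compares active with sham stimulation. The primary outcome (Section 3.3) and the Aim 1 analysis (Section 11.1) compare migraine patients with healthy controls on baseline µOR BP_ND and on its change during the pain challenge. Neither section divides the migraine patients by arm.

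On numbers, Section 4 says "if episodic migraine (n=60), they will be randomized to one of two treatment arms", with 30 in each. For controls it says "We will then recruit healthy volunteers to a total of 30 age- and gender-matched healthy subjects", of whom up to 10 come from an earlier project. Section 14.4 is consistent with this: "20 gender- and age-matched healthy controls" are to be recruited, and 10 more are brought in.

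On timing, Schematic of Study Design II notes "Healthy volunteers complete participation after PET/MRI#1 visit". Section 7.3 and Appendix A place PET #1 before Day 0, when stimulation starts. Table 1 in Section 8.1.3 gives all three groups the same PET protocol.

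**The concern.** Controls have only one scan, so the Aim 1 group comparison can be made only at PET #1. The active and sham arms have received nothing by then and are, for this purpose, a single migraine group. Halving that group has no basis in the design. Loss during stimulation or follow-up cannot remove a first scan already acquired, so the study-wide 20% allowance does not carry over to Aim 1 automatically.

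Section 11.2 is the only place that sizes the primary outcome, and it describes a different comparison. A null Aim 1 result would then be read against the wrong sensitivity: the plan implies that differences below 1.2 SD fall short of 80% power, whereas the design reaches 80% at roughly half that difference.

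**Working it through.** **Inputs.** Section 11.2: two-group t-test, two-sided 0.05, 80% power, effect size 1.2, 24 per group, 20% dropout. Section 4: 60 migraine patients and 30 controls.

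**Formulas.** For group sizes n1 and n2 and standardised difference d:
- Standard error in SD units: SE = √(1/n1 + 1/n2)
- Power from the noncentral t with n1 + n2 − 2 degrees of freedom and noncentrality d/SE
- Detectable difference: the d at which that power is 80%. The normal approximation, (1.960 + 0.842) × SE, is a check.

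**Step 1: the plan's own figure.**
- The dropout step is right: 30 × 0.8 = 24.
- SE for 24 v 24 is √(2/24) = 0.289, and the noncentrality at 1.2 is 1.2/0.289 = 4.16.
- Power is 98.3% (98.6% by the normal approximation), so the stated 80% does not reproduce.
- At 1.2, 80% power needs 12 per group (80.2%), that is, 24 in total. The plan says 24 in each group.
- With 24 in each group, the detectable difference at 80% power is 0.826 (check: 2.802 × 0.289 = 0.81).

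**Step 2: Aim 1 as designed.**
- SE for 60 v 30 is √(1/60 + 1/30) = 0.224.
- The detectable difference at 80% power is 0.633 (check: 2.802 × 0.224 = 0.63).

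**Step 3: range if some first scans or controls are not usable.** The documents give no rate of loss before PET #1, so these rows are assumptions. A 20% loss leaves 60 × 0.8 = 48 patients and 30 × 0.8 = 24 controls. The last row omits the 10 earlier-project controls.

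| Migraine v control | SE (SD units) | Detectable d, 80% power | Power at 1.2 |
|---|---|---|---|
| 24 v 24 (as in Section 11.2) | 0.289 | 0.83 | 98.3% |
| 60 v 30 | 0.224 | 0.63 | 99.96% |
| 48 v 30 | 0.233 | 0.66 | 99.9% |
| 60 v 24 | 0.242 | 0.68 | 99.8% |
| 48 v 24 | 0.250 | 0.71 | 99.7% |
| 60 v 20 | 0.258 | 0.73 | 99.6% |

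**Step 4: splitting the gap.** From the stated 1.2 to 0.63, about 0.37 (1.20 − 0.83) comes from the effect size not matching 24 v 24. About 0.19 (0.826 − 0.633) comes from using the wrong group sizes for Aim 1.

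**The case against.** The best defence is that both errors are conservative. If 24 v 24 is enough, 60 v 30 is more than enough; at the stated 1.2, power moves only from 98.3% to 99.96%. No contrast fails and no enrolment decision changes. That stands, and it makes this a correction to a stated figure rather than a design flaw. A reader might infer from a wrong sample-size statement that the trial is undersized for its primary group comparison; the arithmetic shows the opposite.

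A reader might also infer that an analyst would follow Section 11.2 and discard one migraine arm, losing precision. The documents do not support this. Section 11.2 sizes the study and does not define an analysis set. The Aim 1 analysis in Section 11.1 compares migraine with controls and makes no split by arm. Section 11.6 defers final detail to a Statistical Analysis Plan, listed under Supplemental Materials as a separate document.

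Nor can it be said that no dropout applies to Aim 1. Screening and PET #1 share a three-week window before Day 0 (Sections 7.2 and 7.3). A scan is rescheduled if there was an attack in the preceding 48 hours and may have to be repeated after a technical problem (Section 8.1.3), and Appendix A requires pregnancy and drug screening at the PET visit. Some loss before a usable first scan is possible, which is why 0.63 is a best case and the range is shown.

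Finally, saying that power rises from 80% to about 95% would mislead, because that comparison starts from 0.83 SD, a figure the protocol never states.

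**Conclusion.** The point holds as a conservative misstatement. The sizes and sensitivity in Section 11.2 do not describe the primary Aim 1 comparison, which on the design is up to 60 v 30 at PET #1. Its detectable difference at 80% power is about 0.63 SD, or about 0.71 SD with 20% of first scans lost in both groups. For Aim 2 the 24 v 24 sizing is right, but its detectable difference is about 0.83 SD, not 1.2.

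This rests on four assumptions:
- The pooled 60 v 30 set is inferred from the design and the wording of Aim 1; the plan does not name it as an analysis set.
- The earlier-project controls are treated as exchangeable with new ones; without them the figure is about 0.73 SD.
- The calculation is an unadjusted t-test, whereas Section 11.1 plans a covariate-adjusted mixed model.
- It covers only the group comparison. The primary outcome also includes associations with pain ratings, which Section 11.2 does not size and for which Section 11.1 itself concedes low power.

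**What to change.** - In Section 11.2, give Aim 1 its own sentence: first scans only, both migraine arms pooled, 60 v 30, 80% power for about 0.63 SD by unadjusted two-sided t-test at 0.05, or about 0.71 SD if 20% of first scans in both groups are lost or unusable.
- Keep 24 v 24 for Aim 2 only, and replace the effect size of 1.2 with about 0.83 SD at 80% power.
- In Section 11.1, state that the Aim 1 group comparison pools the two migraine arms before stimulation.
- Add that these figures do not cover the Aim 1 correlations with pain ratings.

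The cost is a few sentences of text. No patients, scans or visits are added.
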